Every effort will be made to conduct the exit interviews in person, but when that is not possible, we will offer the opportunity to complete the exit interview via Zoom, telephone or in writing through email. For electronic administration, first choice delivery will be Zoom followed by telephone or writing through email.

Follow-Up Interview. This takes place for treatment and control groups 30 days after the exit interviews. Here, participants answer a few questions about substance use and journaling since we met with them last. Before this interview, participants will be asked to complete their final Qualtrics questionnaire.

Data Capture. Participants in the treatment group will take a snapshot of their journal entries and upload this image to a Qualtrics survey to affirm that assignments are completed; this skill will be taught and practiced during the screening meeting and Group Phase and practiced during the Independent Practice Phase. Participants will learn how to do this using Qualtrics and smartphones or tablets during group and will be able to continue to use their own smartphones or tablets to continue this practice during The Independent Practice Phase. After uploading the image of their journal, participants will answer psychometric questionnaires in Qualtrics. Study iPads will be physically secured when not at use in a staffed office/

supervised storage space (e.g., cabinet or drawer) at NUWAY. Participants will be asked to complete their journal entries right before they upload them to Qualtrics. Individuals in the control group will simply fill out the Qualtrics surveys at the same schedule as the treatment group.

Participants' written entries into their journals is also data of interest to us, including what they write and how many items they write under each category. NUWAY is outpatient versus our previous host site which was residential so we suspect there will be greater incidence of people arriving to group without their journals (having left them at home for example). Participants will have the option to leave their journals on site at NUWAY with staff in a supervised storage space (e.g., cabinet or drawer). Forgetting one's journal is less of a worry during stay-at-home electronic administration.

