- Assess hypothesized treatment outcomes such as increased treatment retention and decreased recurrence of substance use. Assess hypothesized mediators such as satisfaction with recovery and improved mood. For a complete list, see the measures section.
- Assess feasibility and acceptability of The Group Phase and The Independent Practice Phase for the treatment group.
- Conduct qualitative exit interviews to ascertain participants' subjective experiences of the intervention (treatment group), study logistics, relevance to recovery in rural communities (treatment group), and feasibility and acceptability of the intervention (treatment group). A quantitative Qualtrics survey will also be administered at this meeting.
- Conduct one-month follow up interviews. Ask about substance use and journaling behavior. Participants can participate in follow up interview even if they skip the exit interview for whatever reason. Participants complete the final questionnaire at this time.
- Study and refine recruitment processes, retention ability, functioning of Qualtrics surveys, and feedback about feasibility and acceptability. Create IRB amendments as needed.

5.3. Exit Interview: After the first 5 weeks of the study (for those in the treatment group, this 5 week period aligns to The Group Phase and The

Independent Practice Phase) participants will be invited to participate in a qualitative exit interview with research staff. If the resident has been discharged from NUWAY on good terms during the course of the study, we will reach out to them and invite them to an exit interview. We would contact the person at the forwarding information on file at NUWAY. The participant will have given informed consent for this in the informed consent document. We will meet with participants at NUWAY or in their home or at a local library or other reasonable location that offers privacy (during electronic administration, we will meet with them over Zoom). The research study will pay round trip for a taxi or Uber or similar ride program for the participant to meet us for the Exit Interview (we will not use this option during electronic administration). Participants will also be encouraged to call us to schedule the Exit Interview.

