If participants leave NUWAY on good terms during the study period, they may still be able to continue to be in the study because it is possible to continue study activities from outside of NUWAY for the independent practice phase. Any smartphone or tablet can be used to continue to participate in the independent practice phase. We may reach out to participants who continue to participant in this way to encourage them to continue in the study or ask if they wish to remain in the study using the contact information they provide to use through NUWAY Inc.

Follow up Interview: At approximately 30 days after the exit interview, we will follow up with participants. Zoom is the first choice but a telephone interview is acceptable for this procedure. We will ask participants about any substance use and journaling in the past 30 days. We will ask a few additional qualitative questions such as what was most memorable about being in the research study, and other similar questions. Participants will be encouraged to complete their final Qualtrics survey before this interview.

- 5.4. Individually Identifiable Health Information: Research study staff will meet with NUWAY staff at reasonable intervals to collect data on our primary outcomes: 1) treatment retention and 2) recurrence of substance use. At these occasions we will go through our list of study participants and ask NUWAY staff if: 1) that person has left treatment or been asked to leave; 2) that person has had a positive urine analysis screening indicating recurrence of substance use. We will mark down the replies in our deidentified data file. If the participant cannot remember date of entry into NUWAY, we will also gain this information from NUWAY staff and the treatment record. To facilitate this work, study staff will use a password-protected file linking participants' real names with study IDs (codenames/numbers).

6. This study therefore includes PHI and therefore we have combined our informed consent document with the appropriate text from a HIPAA authorization form.

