13.1. Withdrawal Circumstances: Participants will be withdrawn from the research without their consent for three reasons: 1) if the participant leaves NUWAY treatment against staff advice, 2) if the participant leaves NUWAY treatment at the request of staff for breaking the rules (for example, if they instigate a physical altercation), or 3) the participant leaves NUWAY treatment without discussion with staff and does not return. In these three situations, we would retain the person's data to date and code them as having discontinued treatment, since treatment retention is one of our primary outcomes. Participants of course can keep any Target gift card credits they have earned. If a participant leaves treatment and the study owes the individual Target gift cards, these will be distributed electronically.

13.2. Withdrawal Procedures: Participants can elect to leave the study at any time. This is emphasized in the informed consent document. If participants leave the study, we will still consult NUWAY records to determine relapse or

treatment departure for all study participants. We will include this information in the informed consent document.

Termination Procedures: If a participant stops participating in study activities, we will reach out to them up to 2 times and ask them if they would like to leave the study. If they say no then the process will stop and we will pay them any Target gift cards we owe them. If they are uncertain, we will warmly invite them to return to study activities, but will then consider them to have left the study if they do not return. We may also ask NUWAY staff to help us find out this information. If a person wishes to leave the study, we will note this in our study records. For individuals who leave the study prematurely, we will use data already collected and follow up data on relapse and treatment departure in our data analyses. Participants of course can keep any Target gift card credits they have earned and we will pay out any additional Target gift cards earned upon their exit from the study.

NUWAY study participants will be required to sign a release of information naming research staff, so that research staff and NUWAY staff can communicate with each other. If study participants call research staff by telephone, we will be able to call them back at NUWAY and speak to them or leave a message.

14. Risks to Participants

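### Section 13.1 withdraws bad-terms leavers from the research, so their substance use after exit may go unseen, and unevenly by arm if PPJ changes retention

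*Combined protocol and SAP*

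**What the plan says.** Section 3.1 names rates of substance use and treatment retention as primary outcomes, alongside feasibility and acceptability.

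**Withdrawal.** Section 13.1: "Participants will be withdrawn from the research without their consent for three reasons: 1) if the participant leaves NUWAY treatment against staff advice". Leaving at staff request and leaving without discussion are the other two reasons. I call all three bad-terms exits. For these people the study keeps the data it has and will "code them as having discontinued treatment, since treatment retention is one of our primary outcomes". Nothing is said about coding their substance use.

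**Records.** Section 13.2 still consults NUWAY records for all study participants. Of those who leave the study early it says "we will use data already collected and follow up data on relapse and treatment departure in our data analyses". Under 5.2 (Outcomes) and 20.2, the NUWAY record of recurrence rests on urine tests, other drug screens and self-report made at NUWAY.

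**Contact after leaving.** Section 5.3 describes this for one kind of leaver: "If the resident has been discharged from NUWAY on good terms during the course of the study, we will reach out to them", and "If participants leave NUWAY on good terms during the study period, they may still be able to continue to be in the study". Other provisions are broader. Section 5.2 offers drop-outs an abbreviated exit interview, and gives people who missed an interview a combined script. Its list of procedural steps adds: "Participants can participate in follow up interview even if they skip the exit interview for whatever reason". Section 9.3 collects two contact people per participant, to help invite them to both interviews. None of these says whether someone withdrawn under 13.1 is included.

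**The concern.** Section 13.1 secures one primary outcome and is silent on the other. Retention is fully coded for a bad-terms leaver. Recurrence after exit is not, because the NUWAY record would generally gain nothing once the person has gone. That is equally true of good-terms leavers, but for them 5.3 provides a route to the interviews. For bad-terms leavers, a literal reading of 13.1 closes that route.

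What removes the data is leaving treatment, which PPJ is itself hypothesised to change (section 1, Objectives). If PPJ keeps more people in treatment, more unseen use falls in the control arm and a benefit on substance use is partly hidden. If PPJ lowered retention, the sign would reverse. If retention is equal, the arms lose about the same, though recurrence could be understated in both. Under 17.3 the descriptive statistics from this pilot will be used to size a larger trial, so a distorted rate or difference would carry forward.

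**Working it through.** **1. The plan's own figures.** Section 17.2 uses N = 76, taken here as 38 per arm (1:1 is an assumption). With h = 2·arcsin√p₁ − 2·arcsin√p₂ and power = Φ(h·√(n/2) − z):

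| Outcome | Rates | Test | Stated | Recomputed |
|---|---|---|---|---|
| Abstinence | 41.5% v 24.8% | 1-tailed .10 | .61 | .609 |
| Abstinence | 41.5% v 24.8% | 2-tailed .05 | .34 | .344 |
| Retention | 96.6% v 75.9% | 1-tailed .10 | .94 | .942 |
| Retention | 96.6% v 75.9% | 2-tailed .05 | .82 | .815 |

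The figures reproduce, so the rates below are read as the plan uses them. The abstinence difference is 41.5 − 24.8 = 16.7 points.

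**2. Exits by arm on those rates.** Treat everyone not retained as a bad-terms exit (an assumption). PPJ: 100 − 96.6 = 3.4%. Control: 100 − 75.9 = 24.1%. Difference: d = 20.7 points. With 50 per arm (about 100 people, all randomised 1:1, also assumed) that is 1.7 v about 12 people.

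**3. Hidden gap.** Let u be the share of leavers whose only use is after exit and unseen, equal in both arms. If unseen use is counted as no use, each arm's recorded use falls short by (exit rate × u), so the hidden between-arm gap is d × u. The plan gives no rule for unseen use. If such cases were set to missing, this formula would not apply.

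| u | d = 0 | d = 10 points | d = 20.7 points |
|---|---|---|---|
| 0 | 0 | 0 | 0 |
| 25% | 0 | 2.5 | 5.2 |
| 50% | 0 | 5.0 | 10.4 |
| 75% | 0 | 7.5 | 15.5 |
| 100% | 0 | 10.0 | 20.7 |

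**4. A hypothetical example.** Suppose 30% of stayers in both arms use, 75% of leavers use, and half of the leavers' use is recorded before exit, so u = 0.375.
- True use, PPJ: 0.966 × 0.30 + 0.034 × 0.75 = 31.5%. Control: 0.759 × 0.30 + 0.241 × 0.75 = 40.8%. Difference: 9.3 points.
- Recorded use: 30.3% v 31.8%. Difference: 1.6 points (from unrounded values).
- Hidden: 20.7 × 0.375 = 7.8 points.

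**5. What the documents offer on u.** In the development study (2.2, Relevant Study #3), 4 of 15 left on other than good terms: 3 with recorded use and 1 without. The share without recorded use is 1/4 = 25%, exact 95% interval 0.6% to 81%. That study had 15 women, a residential site and no control group. It illustrates u and does not estimate it for this trial.

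**The case against.** The strongest reply is that the plan already reaches many of these people. Section 13.2 keeps the record check for everyone and plans to use follow-up data on relapse. Section 5.2 invites drop-outs to an abbreviated interview and opens the follow-up interview to those who skipped the exit interview. Section 9.3 collects contacts with no exception by discharge type. The good-terms wording in 5.3 does not bar anyone else. The interview scripts and the consent form are not in the text available, and may settle it.

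Much of that stands. A reader might infer that 13.1 forbids interviewing bad-terms leavers, or that all their substance-use data are lost. The documents support neither: use recorded up to exit is kept, and the interview provisions may cover some of these people. What remains is that 13.1 withdraws them from the research, no passage says the interview offers override it, and the record check cannot recover use after exit.

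Two other inferences also fail. One is that the single leaver of four without recorded use caps the share at 25%; with four people it caps nothing. The other is that someone who misses the exit interview has a stretch of time that no question covers. Section 5.3 says "We will ask participants about any substance use and journaling in the past 30 days" and 5.2 says "Here, participants answer a few questions about substance use and journaling since we met with them last", but those who miss the exit interview get a combined script that cannot be seen here. For those who attend both interviews the two windows are about the same.

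It is also fair that the consequence is modest. The main objective is feasibility, and the plan disclaims power for group comparisons. At 50 per arm on the 17.2 abstinence rates, the 95% half-width is 1.96 × √(0.415 × 0.585/50 + 0.248 × 0.752/50) = 18 points, wider than most of the gaps above. If PPJ improves retention, the bias works against PPJ. This limits the severity. It does not justify leaving a cheap ambiguity in a primary outcome.

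**Conclusion.** The point holds as a should-fix matter, with medium confidence. Read literally, 13.1 ends interview follow-up of substance use for people who leave on bad terms, and the provisions that might reach them are not reconciled with it. The loss differs by arm only if PPJ changes retention.

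The size is unknown. It is zero if all leavers' use is on record before exit. On the 17.2 retention difference it is about 5 points at a 25% share and 10 at 50%. This assumes that unseen use is counted as no use, that the share is equal in both arms, and that everyone not retained is a bad-terms exit. The retention rates are borrowed from earlier behavioural activation work and are not data from this trial.

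**What to change.** - Amend 13.1 so that these exits stop study activities but not outcome follow-up. No rule on treatment or discharge changes.
- Invite every randomised participant to the exit and 30-day interviews whatever the discharge type, unless they decline, using the contacts collected under 9.3.
- Reconcile 13.1 and 5.3 with the drop-out and combined-interview provisions in 5.2 and the contact provision in 9.3.
- Treat recurrence after exit without data as unknown, not as no use.
- Report the number of such exits by arm, with one sensitivity analysis that counts them as recurrence. State that this analysis carries any retention effect into the substance-use result.
- As minor wording, align the follow-up window between 5.2 and 5.3. Also align 5.4, which asks NUWAY only about positive urine tests, with 5.2 and 20.2, which also count other screens and self-report.

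Cost: protocol and consent wording, a few contact attempts, a small extra analysis, and up to $20 in gift cards per person ($10 for each interview under 12.5). If exits ran at the development study's 4/15, 100 × 4/15 ≈ 27 people, and 27 × $20 = $540 if all took both interviews.

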14.2. Reproduction Risks: N/A

14.3. Risks to Others: One group exercise we will employ is "each one teach one."

In this exercise, group members are invited to choose someone in their supportive network to teach the journaling practice to. This secondary person would be invited by the participant to try PPJ, and then the "teacher" and the friend will share contents of PPJ with each other. We do not expect that the secondary participant would face any risks beyond mild and temporary feelings of discomfort that might arise when reviewing the past 24 hours or planning the upcoming 24 hours.

15. Incomplete Disclosure or Deception

15.1. Incomplete Disclosure or Deception: N/A. Participants will be informed that this is a study of journaling in recovery.

16. Potential Benefits to Participants

16.1. Potential Benefits: The hypothesized benefit of the proposed study is the potential of improving satisfaction with life in recovery and increasing other wellbeing factors (e.g., positive emotion), which we hypothesize will support sustained abstinence from alcohol and other illicit drugs and sustained enrollment in the NUWAY treatment center. However, while there

is evidence that gratitude practices and activity planning may yield such benefits, there is no evidence for the benefits of the combined elements that comprise PPJ. The control group will receive the journal and brief instructions for using it and access to the YouTube videos that describe how to use the journals at the exit interview and therefore they may experience some of these benefits. However, in our previous research, participants told us that they felt that the completion of the PANAS instrument to assess mood felt therapeutic.⁶⁰

Although potential risks include frustration, existing psychological withdrawal effects from alcohol and substance use abstinence, mild discomfort when filling out questionnaires, and adjusting to a new lifestyle, these are not life threatening and will subside as treatment progresses.

Finally, issues of confidentiality are a high priority and will be closely monitored throughout the treatment study. Consequently, the risk to benefit ratio in the proposed study appears to be acceptable.

17. Data Management

17.1. Data Analysis Plan: Please see “Analysis Plan” under 5.2, above.

17.2. Power Analysis: Preliminary data from existing behavioral activation (BA) research was used to determine power for the original proposal with N=76. For the outcome of abstinence (yes/no), previous work found outcomes for this variable of 41.5% for the BA group and 24.8% in the control group.¹⁴ For a 1-tailed test with $p < .10$, our power to detect a significant effect for abstinence (yes/no) in the proposed study would be .61 (for a 2-tailed test with $p < .05$, power would be .34). For the outcome of treatment retention (yes/no), previous work showed 96.6% for the BA group and 75.9% in the control group.¹⁶ For a 1-tailed test with $p < .10$, our power to detect a significant effect for treatment retention (yes/no) in the current study would be 94% (for a 2-tailed test with $p < .05$, power would be .82). Therefore, we should be adequately powered to detect statistically significant differences for the outcome of treatment retention in the current study using a 2-tailed test. R was used to conduct these power analyses.⁶¹

17.3. Statistical Analysis: This pilot study will not be adequately powered to detect an effect. Still we will compare the treatment and control groups using t tests and multi-level models to determine differences in means and in slopes between the groups, respectively. Descriptive statistics of the quantitative measures will be used to conduct power analyses and sample size calculations for a larger controlled trial. Also, multi-level analyses will

be conducted to determine significant change over time in factors of interest. We will also be able to examine whether change over time varied by certain subgroups (e.g., those with lower versus higher levels of the factor of interest at baseline).

17.4. Data Integrity: The use of Qualtrics to collect survey data will improve data accuracy because this allows us to avoid keystroke and other errors involved with manual data entry from written questionnaires. We will scrutinize the data produced by Qualtrics to ensure its integrity; whether values are within scale ranges and whether missing data is coded correctly. We will carefully examine and clean the data to ensure accuracy. For standardized instruments, we will be very careful to follow the directions for summing or taking the mean of scale items and reverse code any items as per the instructions.

18. Confidentiality

18.1. Data Security: We will safeguard against breaches of confidentiality by coding participant data by codename or number rather than by name and by keeping information linking these codenames or numbers to research staff via password protected electronic file. Further, no individuals will be identified by name nor will any identifying information be offered when presenting data in lectures, seminars, professional presentations, or papers. When qualitative data are transcribed, whether from exit interviews or recorded group sessions, they will be de-identified to replace any spoken names or identifiers with brackets, e.g., "Joan" will be replaced with "[Participant's Daughter]."

The Office of Measurement Services (OMS) of the University of Minnesota will be assisting the study by designing the Qualtrics mechanism that we will use for data collection. OMS has many years of experience in collecting, maintaining, and storing data in accordance with FERPA and HIPAA regulations. OMS's internal security and safeguards go beyond the minimum levels established for the University of Minnesota. OMS provides data security and privacy protection by using a dedicated server to store data, by performing daily data back-ups, and by using Secure Sockets Layer (SSL), the industry-standard means for safeguarding web communications. OMS also utilizes encryption protocols for the storage and transmission of data which further ensures data security. Additionally, OMS recently completed IT risk assessments from Berry Dunn and Deloitte to verify that our data handling and storage procedures are up to date and effective.

NUWAY will make mention in chart notes if and when clients have participated in PPJ groups.

Since this research is being funded by the National Institutes of Health, it is automatically issued a Certificates of Confidentiality (CoC). The CoC protects the privacy of research participants by prohibiting disclosure of identifiable, sensitive research information to anyone not connected to the research except when the participant consents or in the following situations: (1) The Certificate cannot be used to resist a demand for information from personnel of the United States Government that is used for auditing or evaluation of Federally funded projects or for information that must be disclosed in order to meet the requirements of the Federal Food and Drug Administration (FDA). (2) The Certificate of Confidentiality will not be used to prevent disclosure to state or local authorities of child abuse and neglect, or harm to self or others.

19. Provisions to Monitor the Data to Ensure the Safety of Participants

19.1. Data Integrity Monitoring:

The job of data integrity monitoring will be conducted by PI [name]. She will oversee all study progress and ensure that the study is conducted, recorded, and reported in accordance with the protocol and standard operating procedures. In the event that changes to the protocol are needed, PI [name] will make modifications using standard IRB procedures. PI [name] is an Associate Professor of Social Work and has been employed by the University of Minnesota since 2013. PI [name] has expertise in positive psychology,^{62,63} gratitude,^{17,22} and spirituality in AUD recovery;^{64–67} as well as qualitative data analysis;^{17,60} quantitative data analysis;^{64,65,68} mechanisms of behavior change;⁶⁴ and the conduct of randomized control trials to test novel interventions to support AUD recovery.^{17,69} PI [name] will be in ongoing contact with staff at NUWAY, specifically [name], Chief Clinical Officer of NUWAY, and the NUWAY site supervisor, who will be the study's primary contacts at the host agency. PI [name] will supervise study staff including all Research Assistants. Supervision will involve face to face meetings at a minimum of once every two weeks. Study reports will be provided to the IRB according to the regularly scheduled requirements of such reporting. In these reports we will describe recruitment progress and study findings as they unfold.

19.2. Data Safety Monitoring:

All research staff will complete the online training modules which cover HIPAA, ethical research with human subjects, accuracy, record keeping, and confidentiality. These modules are offered by the University of Minnesota and include HIPAA Training and the Collaborative Institutional Training Initiative (CITI) Program's Social/Behavioral or Humanist Research

PROTOCOL TITLE: Journaling and Addiction Recovery

VERSION DATE: 13 April 2021

Investigators and Key Personnel curriculum. PI [name] will model and extensively review this content with all staff.

Safety.

As noted in the human subjects section of this application, we will protect against physical and emotional symptoms resulting from substance use abstinence and any other relevant psychological symptoms. Further, we are acutely aware of the importance of protecting participant confidentiality and in abiding by HIPAA guidelines.

The baseline session will take place in a private and quiet setting at NUWAY, or, with electronic administration, on a Zoom call but we will make sure the participant is in a quiet, private place and will encourage them to use headphones. The meeting will begin with screening informed consent, screening, and then informed consent, which will include a detailed description of the purpose and procedure of the study, emphasizing our policy regarding privacy and confidentiality, and an opportunity for the individual to ask any questions or voice any concerns. A screening informed consent document will be signed before screening activities take place. A regular informed consent document will be reviewed and a quiz on its contents passed before any study data are collected. Documents will be signed electronically. We will invite and answer any questions about the study. We will make sure the participant understands the information and does not feel pressured to make a decision. Participants will understand that their participation is entirely voluntary.

Aside from signing the consent forms, and the “codename” form, The participants’ name will be retained in REDCap but all other data (from the Qualtrics surveys for example) will be separated from the participant’s name; only research staff will have access to a document(s) that links participant number/codename and name. All of the information obtained from subjects is entirely for research purposes and quoted by codename or number and kept in locked confidential files at our offices at the University of Minnesota or on password protected laptops or university servers. This information is not available to anyone except the investigators.

Although our sample participants will have been in treatment a minimum of 2 weeks and no longer suffering from the acute physical withdrawal effects of alcohol or drug abstinence, continued abstinence from drugs and alcohol is often associated with irritability, restlessness, anxiety, depressed mood, sleep disturbance, increased appetite, and decreased concentration. Abstinence also may exacerbate pre-existing conditions. Although these symptoms may be effectively treated with appropriate intervention, we will monitor these symptoms at each session. Individuals reporting moderate or persistent concerns or problems will be referred by study staff to appropriate medical/psychiatric staff at NUWAY. We will periodically

evaluate the data collected regarding both harms and benefits to determine whether participants remain safe.

Study Research Assistants or PI [name] will review the data, especially the pictures of the journal entries, as soon as possible after submission but no later than 72 hours after submission to examine the data for any safety concerns.

If participants experience distress related to the baseline questionnaire, including the question that asks about history of trauma, we will refer them to NUWAY staff.

We will use the Zoom waiting room feature and we will only admit group members into the Zoom room. If a group member behaves inappropriately (e.g., shares inappropriate words or images, i.e., Zoom bombing) we will remove them from the Zoom room.

20. Provisions to Protect the Privacy Interests of Participants

20.1. Protecting Privacy: REDCap information will contain the participant's name but all other documents in paper or electronic format will include the person's codename or number only. An electronic file matching participant name to codename or number will be kept on a password protected computers and the file itself will be password protected and erased one year after the conclusion of data analysis. Any paper copies of this information will also be destroyed at this time.

We will go to great lengths to make sure participants understand the nature of the research study and our concern about their privacy. This will be made clear in the content of the informed consent document. We will review this information with participants in depth as we go over all elements of the informed consent process. We will assure the participant that we will do everything we can to ensure their privacy, including using a codename or number associated with their data and putting a password on the electronic file that matches their codename or number to their name. Limitations to confidentiality will also be described, such as whether the participant describes the desire to harm themselves or others, or whether a minor or vulnerable adult is at risk of abuse or neglect. We will ask that participants use a quiet, private room for Zoom meetings and use headphones if at all possible during our Zoom class with them.

20.2. Access to Participants: The research team will not have access to NUWAY records. To determine our key outcomes, recurrence of substance use or discontinuation of treatment, a NUWAY staff member will meet with a member of the research team at reasonable time intervals to share whether participants have left treatment or whether they have resumed

substance use. Resumption of substance use is confirmed at NUWAY via urine testing or other drug screening or client self-report. Results of these tests, if positive for substances, will be communicated to research staff at reasonable periods and we will code this information into our de-identified data records. We will also have staff check the NUWAY record if the individual does not remember the date they started at NUWAY.

21. Compensation for Research-Related Injury

